3.4.2 Study Product/Treatment

The study product is Sensodyne Repair and Protect (US market), an anti-sensitivity toothpaste containing 0.454% SnF2.

3.4.3 Study Period

The duration of the study is defined for each participant as the date that the signed eIC is provided through the end of the study follow-up period 168 days (± 7days), participant death, early withdrawal from the study, lost to follow-up or overall study termination.

4. Statistical Analysis

4.1 Sample Size Calculation

Sufficient participants will be screened (to allow for up to 50% screen failure rate) to ensure approximately 500 participants are enrolled and approximately 400 complete (to allow for up to 20% drop-out rate).

A sample size of 400 participants would ensure at least 90% power to achieve a statistically significant (two-sided 5% significance level) reduction in Baseline in DHEQ Total Score when using a one-sample t-test, assuming a true population effect size (mean reduction/standard deviation [SD]) of 0.2. The planned primary analyses in this study will use a Mixed Model with Repeated Measures (MMRM) with time point as a fixed effect, Baseline DHEQ score as a covariate and participant as a repeated measure.

CC	HLN-003 Statistical Analysis Plan	
	Page 10 of 17	Version 1.0

As well as providing adequate power to demonstrate statistically significant reductions from Baseline at each timepoint (4, 8, 12, 16, 20 & 24 weeks), 400 participants will ensure adequate precision of the corresponding 95% confidence intervals (Cls) for the mean reduction, and robust RWE relating to the magnitude of benefit from product use, at each timepoint. In a previous study (Haleon study 216953) assessing the same DHEQ-48 endpoints over 24 weeks in a RWE setting for an anti-sensitivity toothpaste containing 5% KNO3, the SD of the change from Baseline in DHEQ Total Score was shown to increase from around 30 units at Week 4 to 50 units at Week 24. An SD of 30 units and 50 units across 400 participants would equate to precision of the 95% Cls for the mean reduction within +/- 3 and 5 units, respectively.

4.2 Endpoints

4.2.1 Primary Endpoints

Change from Baseline in Section 2 DHEQ endpoints at Weeks 4, 8, 12, 16, 20 & 24.

- Total DHEQ score (sum section 2 Q1-34),
- Each of the domain's mean values
 - Restrictions sum Q1-4
 - Adaptation sum Q5-16
 - Social Impact sum Q17-21
 - Emotional Impact sum Q22-29
 - Identity sum Q30-34

4.2.2 Secondary Endpoints

- Change from Baseline in additional DHEQ endpoints at Weeks 4, 8, 12, 16, 20 & 24.
 - Section 1:
 - Impact on Everyday Life (Q1-3, individually)
 - Section 2:
 - Global Oral Health Score (Q35)
 - Effect on Life Overall Score (Sum Q36-39)
- Percentage (%) of participants who 'agree' (score 5-7) with each item (statement) in the 5 DHEQ domains (DHEQ Section 2, Q1-34) at baseline and week 24.
- Change from Baseline in NPRS score at Weeks 1, 2, 4, 8, 12, 16, 20 & 24.
- Satisfaction Numerical Rating Scale (NRS) at Week 24.
- Oral Hygiene Questionnaire (OHQ) responses at Baseline.

4.2.3 Safety Endpoints

- Treatment Emergent Adverse Events reported over the study period.
- Treatment Emergent Oral Related Adverse Events.
- Treatment Emergent Serious Adverse Events.

HLN-003 Statistical Analysis Plan		
Page 11 of 17	Version 1.0	

4.3 Analysis

4.3.1 General Considerations

All statistical evaluations will be conducted using SAS® version 9.4 or higher (SAS® Institute, Cary, North Carolina) or R version 4.03 or higher (© The R Foundation). All tables, figures and listings will be produced in landscape format.

4.3.2 Data Display

In general, all data will be listed by subject and visit/time point where appropriate. The total number of subjects under the stated population (N) will be displayed in the header of summary tables.

Data will be summarized using descriptive statistics for continuous variables. Unless otherwise specified, descriptive statistics will include number of subjects, mean, standard deviation, standard error, minimum, median, and maximum. The minimum and maximum statistics will be presented to the same number of decimal places as the original data. The mean and median will be presented to one more decimal place than the original data, whereas the standard deviation and standard error will be presented to two more decimal places than the original data.

In summary tables of categorical variables, counts and percentages will be used. Descriptive summaries of categorical endpoints will include counts (missing and non-missing) and percentage (%) out of the participants with non-missing data.

P-values will be displayed with 4 decimals, e.g., p=0.0001 and p-values below 0.0001 will be displayed as p<0.0001.

In by-visit summary tables only scheduled visits/timepoints will be summarized. In listings, all visits and timepoints with any data collected will be included.

The change from baseline values will be derived for each subject as the post-baseline evaluation minus the baseline evaluation.

All dates will be displayed in ISO 8601 date format (YYYY-MM-DD).

Residual analyses will be conducted for each MMRM applied.

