### 8.2 Study Period

### 8.2.1 Week 0 (Baseline)

Participants must complete the following Baseline activities within 14 days of enrollment to be able to continue in the study.

- Complete DHEQ-48
- Complete NPRS
- Complete OHQ
- Record any changes in their health/medical occurrences; record any changes to their
  existing medications/treatments and any new medications/ treatments (including reason
  for use, unit dose, daily dose, start and stop dates, where known and as appropriate).

Study toothpaste will only be shipped to those participants who complete all 'Baseline' activities. Participants will confirm receipt of their study toothpaste in the confirmation of receipt = Day 0) and will be instructed to start using it on the same day.

### 8.2.2 Weeks 1 and 2

- Complete NPRS
- Record any changes in health/medical occurrences; record any changes to existing
  medications/treatments and any new medications/ treatments (including reason for use,
  unit dose, daily dose, start and stop dates, where known and as appropriate).

### 8.2.3 Weeks 4, 8, 12, 16 and 20

- Complete DHEQ-48
- Complete NPRS
- Record any changes in health/medical occurrences; record any changes to existing
  medications/treatments and any new medications/ treatments (including reason for use,
  unit dose, daily dose, start and stop dates, where known and as appropriate).

### 8.2.4 Week 24

- Complete DHEQ-48
- Complete NPRS
- Complete Treatment Satisfaction NRS
- Record any changes in health/medical occurrences; record any changes to existing
  medications/treatments and any new medications/ treatments (including reason for use,
  unit dose, daily dose, start and stop dates, where known and as appropriate).
- Complete EOS and 'open-ended survey' questions.

Property of Haleon- Confidential

HALEON

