3.3 Study Objective

This study will be considered successful if a trend of improvement in OHrQoL is observed over the 24-week treatment period; however, it is expected that statistically significant improvements from Baseline will be observed in DHEQ endpoints, particularly DHEQ Total Score.

Primary Objective

The primary objective of this study is:

• To describe changes in OHrQoL over 24 weeks use of an anti-sensitivity toothpaste containing 0.454% SnF2, as measured by the Dentin Hypersensitivity Experience Questionnaire (DHEQ-48: Total Score and Domain Scores), in a DH population.

Secondary Objectives

The secondary objective of this study are:

- To describe changes in OHrQoL over 24 weeks use of an anti-sensitivity toothpaste containing 0.454% SnF2, as measured by the DHEQ-48 (other endpoints), in a DH population.
- To summarize the individual DHEQ domain items of concern in a DH population before and after 24 weeks use of an anti-sensitivity toothpaste containing 0.454% SnF2.
- To describe changes in the intensity of self-reported DH pain over 24 weeks use of an anti-sensitivity toothpaste containing 0.454% SnF2, as measured by a Numeric Pain Rating Scale (NPRS), in a DH population.
- To describe participant satisfaction with the DH treatment (anti-sensitivity toothpaste containing 0.454% SnF2), as measured by a Satisfaction Numeric Rating Scale (NRS).
- To describe the oral hygiene habits of a DH population using an oral hygiene questionnaire (OHQ).

HLN-003 Statistical Analysis Plan		
Page 9 of 17	Version 1.0	

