3.4.1 Study Population

Sufficient participants will be screened (to allow for up to 50% screen failure rate) to ensure approximately 500 participants are enrolled and approximately 400 complete (to allow for up to 20% drop-out rate).

An enrolled participant is one who has agreed to participate in the RWE study following completion of the electronic informed consent (eIC) process and has successfully met the eligibility criteria to proceed beyond the screening procedures, as applicable for the protocol design.

Eligibility to participate in this RWE study will be reviewed and documented by an appropriate member of the CCI study team before a participant is included in the study.

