4.3.3 Populations to be Analyzed

For the purposes of analysis, the following analysis sets are defined:

The Screened population will include participants who electronically sign the eIC and enter the screening process for assessment of inclusion and exclusion criteria.

The Enrolled population will include all participants who meet the inclusion/exclusion criteria as identified by their responses to the screening questionnaire.

HLN-003 Statistical Analysis Plan	
Page 12 of 17	Version 1.0

The Safety population will include all enrolled participants who complete at least one use of study product (at least one entry in Brushing Diary). Safety population will be used for the analysis of AEs.

The modified Intent-To-Treat (mITT) population will include all participants in the Safety population who have at least one post-baseline derived DHEQ Total Score. Efficacy data will be analyzed using the mITT population only.

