4.3.12 Secondary Objectives Analysis

4.3.12.1 DHEQ, Secondary Endpoints

Change from Baseline will be calculated at each post-Baseline time point (4, 8, 12, 16, 20 & 24 weeks) for the secondary DHEQ endpoints:

- Section 1
 - Change from Baseline in Impact on Everyday Life: Q1, Q2, & Q3 (separate scores)
- Section 2
 - Change from Baseline in DHEQ Global Oral Health (Q35)
 - Change from Baseline in DHEQ Effect on Life Overall (sum of Q36-Q39)

Each DHEQ endpoint listed above will be analyzed using a MMRM with time point fitted as a fixed effect, the respective Baseline score as a covariate and participant fitted as a repeated measure with unstructured covariance matrix. Kenward-Rogers degrees of freedom will be applied. The estimates of the adjusted mean (SE) change from Baseline at each post-Baseline timepoint will be presented along with 95% Cls.

For each DHEQ endpoint listed above (Sections 4.3.13 and 4.3.14), and each individual DHEQ question, the score at each timepoint (including Baseline) and the corresponding change from Baseline (at each post-Baseline timepoint) will be summarized descriptively.

HLN-003 Statistical Analysis Plan	
Page 15 of 17	Version 1.0

Plots of mean score (SE) for each DHEQ endpoint listed above, and the individual DHEQ questions, over time will also be provided.

The number and percentage (%) of participants who 'agree' (score 5-7) with the 34 items (statements) in 5 domains of the DHEQ (Section 2, Q1-Q34) will be summarized at Baseline and Week 24. The percentage for each item will be summarized and presented in descending order of percentage at baseline.

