4.3.15 Missing Values

Missing data due to dropouts/withdrawals will be assessed on an ongoing basis during the study.

For the DHEQ data, for any timepoint if response is missing, it will be excluded from the primary analysis; the data available for each participant (even though some time points may be missing) will still be included in the analysis.

The MMRM approach will include all participants in the mITT population in the analysis. Any missing data from such participants will be treated as 'missing at random', i.e., their missing data at a particular time point will be assumed to behave in similar fashion to a participant with non-missing data at that time point who has similar data at other time points. This approach ensures an unbiased approach to handling missing data under the 'missing at random' assumption.

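### The item 'agree' percentages at Baseline and Week 24 have nested but unequal denominators, so a change in who answers can shift the before/after comparison even if nobody changes

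*SAP*

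**What the plan says.** One secondary objective in SAP 3.3 is to summarize the "individual DHEQ domain items of concern in a DH population before and after 24 weeks use" of the toothpaste. For this, SAP 4.3.12.1 counts participants scoring 5 to 7 on each of the 34 Section 2 items. These counts and percentages "will be summarized at Baseline and Week 24", with items ranked by their Baseline percentage. SAP 4.3.2 sets the denominator for categorical endpoints as the "percentage (%) out of the participants with non-missing data", alongside counts of missing and non-missing; Protocol 12.3 has the same rule.

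Efficacy data use mITT only. Under SAP 4.3.3 this means members of the Safety population "who have at least one post-baseline derived DHEQ Total Score"; a Week 24 score is not required. Protocol 8.2.1 makes Baseline nearly complete by design: "Study toothpaste will only be shipped to those participants who complete" every Baseline activity, and the DHEQ-48 is one of them. Protocol section 8 bars late entry for a missed visit. SAP 3.4.1 plans for about 500 enrolled, about 400 completing and dropout of up to 20%.

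Two provisions come close to the issue. For "each individual DHEQ question, the score at each timepoint (including Baseline) and the corresponding change from Baseline", SAP 4.3.12.1 plans descriptive summaries. On missing data, SAP 4.3.15 says "The MMRM approach will include all participants in the mITT population in the analysis" and assumes missingness at random.

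**The concern.** Taken together, these rules give the two agree columns different denominators. The sets are nested: everyone answering at Week 24 also answered at Baseline, but not the reverse. If participants who stop answering agreed more with an item at Baseline than those who stay, the Week 24 percentage falls below the Baseline one with no individual improving. If they agreed less, it rises.

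The objective is worded as before and after, and there is no control arm, so readers will set the two columns side by side. From those columns alone they cannot separate change within people from change in who answered. The same people are lost for every item, so the shift could run the same way across many of the 34 rows. What is at stake is the reading of one descriptive secondary table.

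**Working it through.** **Plan's own figure.** 400/(1 - 0.20) = 500, so the enrolment target reproduces.

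**Inputs from the documents.** About 400 completers of about 500 enrolled; percentages over non-missing responses; mITT entry on one post-baseline Total Score; Baseline required before shipping.

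**Assumed inputs.** The documents give no item agreement rates, mITT size or profile of those lost. I take 400 responses at Week 24 and mITT sizes N of 420, 450 and 500. The last is the extreme in which every enrolled participant enters mITT. Anyone lost before a first post-baseline DHEQ is outside mITT at both visits, which makes N smaller.

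**Identity.** The displayed difference splits into two parts:

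Week 24 % (responders) - Baseline % (all mITT) = [Week 24 % - Baseline %, both in responders] + [Baseline % in responders - Baseline % in all mITT].

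The second bracket is the denominator shift. It equals -(N - 400)/N x gap, where gap = Baseline agreement in those lost minus that in those retained.

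**Size of the shift, in percentage points (apparent fall when the gap is positive):**

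| Assumed mITT N | Share without Week 24 | Gap 5 | Gap 10 | Gap 20 |
|---|---|---|---|---|
| 420 | 20/420 = 0.048 | 0.24 | 0.48 | 0.95 |
| 450 | 50/450 = 0.111 | 0.56 | 1.11 | 2.22 |
| 500 | 100/500 = 0.200 | 1.0 | 2.0 | 4.0 |

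A gap of 0 gives 0. At N = 500, a gap of -20 gives an apparent rise of 4.0, and a gap of 40 gives a fall of 8.0.

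**Example with nobody changing.** 400 retained at 60% and 50 lost at 80%. Baseline: (400 x 0.60 + 50 x 0.80)/450 = 280/450 = 62.2%. Week 24: 240/400 = 60.0%. The apparent fall is 2.2 points. In the 400 with both responses, the difference is 60.0 - 60.0 = 0.

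**What a same-participant table does not do.** A simulation of 2,000,000 participants assumed 50% agreement at both visits, zero average change, a correlation of 0.6 between visits on the underlying scale, and 20% loss more likely at higher scores:

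- Loss depending on Baseline: planned contrast -3.5 points, same-participant contrast +2.3.
- Loss depending on the Week 24 value: planned contrast -5.8, same-participant contrast -2.3.

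The true change is zero in both. Pairing removes the second bracket of the identity; the first can still be moved by regression to the mean or by outcome-related loss.

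**The case against.** The strongest reply is that the SAP plans no contrast here. It reports two descriptive columns, with no difference, test or interval, and reading them as an effect is the reader's step. Much of the context is also provided. Missing counts show that the denominator changed, each question has a change from Baseline, discontinuation reasons are summarized (SAP 4.3.5), and individual DHEQ data are listed (SAP 4.3.14). Protocol 12.3.6 leaves further missing-data sensitivity analyses to data review. Table layouts sit in TLF shells that were not available, so a same-participant column may already exist there. At the smaller assumed mITT sizes (420 and 450) and gaps of 5 to 20 points, the shift is 0.2 to 2.2 points. The 95% half-width for a single 60% with n = 400 is 1.96 x sqrt(0.60 x 0.40/400) = 4.8 points.

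Most of this stands, and it limits the weight of the point. It does not remove it. Missing counts say how many did not answer, not how they had scored at Baseline. The change scores are within person but on the 1 to 7 scale, so they do not translate into a change in the percentage scoring 5 to 7. The missing-at-random handling works through the MMRM, which is not applied to agree status. The shift is also systematic and can be shared across items, so sampling error of one percentage is not the whole comparison.

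**Conclusion.** The point holds in a limited form. Under the written plan the two agree percentages have nested but unequal denominators, and this alone can move the descriptive comparison. The shift is the share of mITT without Week 24 data times the Baseline agreement gap: about 0.5, 1.1 or 2.0 points per 10-point gap at N = 420, 450 or 500. The mITT sizes, the gap and 400 Week 24 responses are all assumptions.

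Four stronger readings are tempting and are not supported:

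- That a same-participant table would remove the effect of selective dropout. It removes only the denominator shift, as the simulation shows.
- That 4 points is a ceiling. That figure follows from an assumed 20-point gap, and no document bounds the gap.
- That the comparison is biased in the product's favour. Nothing in the documents says who will be lost, and the shift may be zero or reverse.
- That other results share the problem. The primary MMRM and the sample size are unaffected. The NPRS summary of reductions above 30% is within participant, so no denominator mismatch between visits arises there.

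This is a low-cost improvement to one secondary table, not a flaw in the main analysis.

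**What to change.** In SAP 4.3.12.1, and in the matching table shell, add for each of the 34 items the agree count and percentage at Baseline and at Week 24 among participants with both responses. A 2x2 table of Baseline by Week 24 agree status would serve equally well. Keep the all-mITT Baseline column for the ranking. Add a footnote saying that the same-participant figures remove only the shift due to different denominators, describe Week 24 responders only, and do not correct for selective dropout or regression to the mean.

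The cost is a sentence or two in the SAP and a few extra columns for 34 items in an already long table. No new data are needed. If the shells already contain such columns, a sentence in the SAP is enough.

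Separately and optionally, one line in SAP 4.3.12.2 could say how a Baseline NPRS of 0 is treated, because the percent-change formula is undefined there. The planned responder count does not depend on it.

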4.3.3 Populations to be Analyzed

For the purposes of analysis, the following analysis sets are defined:

The Screened population will include participants who electronically sign the eIC and enter the screening process for assessment of inclusion and exclusion criteria.

The Enrolled population will include all participants who meet the inclusion/exclusion criteria as identified by their responses to the screening questionnaire.

HLN-003 Statistical Analysis Plan	
Page 12 of 17	Version 1.0

The Safety population will include all enrolled participants who complete at least one use of study product (at least one entry in Brushing Diary). Safety population will be used for the analysis of AEs.

The modified Intent-To-Treat (mITT) population will include all participants in the Safety population who have at least one post-baseline derived DHEQ Total Score. Efficacy data will be analyzed using the mITT population only.

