### 1.2 Schedule of Activities

The Schedule of Activities (Table 1-1) provides an overview of the study procedures. virtual study team may schedule other (unplanned) interactions, additional to those listed in the schedule of activities, to make assessments required to protect the well-being of study participants.

Haleon Clinical Protocol

HALEON

Protocol Number: 300058

Table 1-1 Schedule of Activities

Procedure	Pre- Screening	Baseline Activities 	Day 0 	Week 1 Day 7 (±1 days)	Week 2 Day 14 (±2 days	Week 4 Day 28 (±7 days)	Week 8 Day 56 (±7 days)	Week 12 Day 84 (±7 days)	Week 16 Day 112 (±7 days)	Week 20 Day 140 (±7 days)	Week 24 Day 168 (±7 days)
Pre-Screening Questionnaire	X										
Confirm Initial Eligibility	X										
eMail invitation to download column app with Unique Participant ID	X										
e-Informed Consent (eIC)		X									
Screening Questionnaire		X									
Demographics		X									
Medical History		X									
Concomitant Medications		X		X	X	X	X	X	X	X	X
Check Inclusion/Exclusion Criteria		X									
Confirm Participant Eligibility 		X									
DHEQ-48 Completion		X				X	X	X	X	X	X
NPRS Completion		X		X	X	X	X	X	X	X	X
OHQ Completion		X									
Study Toothpaste Dispatched 		X									
Participant Confirms Receipt of Study Toothpaste in COLUMN App			X								
Subject Instructed to Start Using Study Toothpaste			X								
DH Treatment Satisfaction NRS Completion											X
Complete End of Study (EOS)/Open Ended											X
Survey Questions											Λ
Self-reported AEs4		X	X	X	X	X	X	X	X	X	X
Study Conclusion											X

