### Footnotes:

- 1. Baseline activities must be completed by participant within 14 days of enrollment.
- 2. Study toothpaste will be dispatched to qualifying participants only after all 'Baseline' activities have been completed.
- 3. Participant will confirm receipt of study toothpaste in the column app (date of confirmation of receipt = Day 0) and will be instructed to start using it on the same day.
- 4. Self-reported changes in health and medical occurrences from immediately after participant provides e-consent signature until the last use of study toothpaste will be recorded as AEs; thus, serious AEs (SAEs) will also be collected from immediately after participant provides e-consent signature until last use of study toothpaste.

Property of Haleon- Confidential

May not be used, divulged, published or otherwise disclosed without the consent of Haleon

HALEON

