### 8 STUDY PROCEDURES

This section describes the procedures to be completed at each planned study timepoint; the order in which procedures should be completed is listed in the Schedule of Activities (Table 1-1).

'Start' and 'expiration' windows will be set for each study-required activity, per timing tolerances specified in the Schedule of Activities (Table 1-1). Access to the CCl app will not be interrupted but outside of these tolerances the participant will not be able to start entering responses or submit late responses for a missed 'visit'. Participants are required to complete at least one post-Baseline DHEQ to be included in the modified Intent-To-Treat (mITT) population.

will provide the app used to conduct all study activities, to provide participants with information and training, and to collect study data. Self-reported adverse events (AEs) will be collected via the collected app.

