**HALEON** 

The Safety population will include all participants who complete at least one use of study product. Safety population will be used for the analysis of AEs.

The modified Intent-To-Treat (mITT) population will include all participants in the Safety population who have at least one post-baseline derived DHEQ Total Score. Efficacy data will be analyzed using the mITT population only.

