4.3.14 Tabulation of Individual Participant Data

Individual participant data will be listed. The enrolled population data will include information on subject disposition, demographic and baseline characteristics, and protocol deviations. The safety population will include brushing diary, concomitant medications, medical history, adverse events, and serious adverse events. The modified intention-to-treat (mITT) population will include Dentin Hypersensitivity Experience Questionnaire (DHEQ),

HLN-003 Statistical Analysis Plan	
Page 16 of 17	Version 1.0

Numeric Pain Rating Scale (NPRS), Numeric Rating Scale (NRS), and the Oral Hygiene Questionnaire (OHQ).

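### Week 1 and Week 2 pain scores are left out of the NPRS analysis for anyone who never gives a post-baseline DHEQ (minor; direction unknown; a SAP-only edit suffices)

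*SAP*

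**What the plan says.** SAP 4.3.3 builds the mITT population from Safety participants "who have at least one post-baseline derived DHEQ Total Score. Efficacy data will be analyzed using the mITT population only". Protocol 12.2.1 has the same definition and also states "Efficacy data will be analyzed using the mITT population only". Protocol section 8 repeats the entry condition: "Participants are required to complete at least one post-Baseline DHEQ to be included in the modified Intent-To-Treat (mITT) population".

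Neither document names the NPRS population in one direct sentence, but three places together lead to mITT:

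- SAP 4.2.2 lists change in NPRS as a secondary endpoint, with Weeks 1 and 2 among its timepoints.
- SAP 4.2.3 lists only adverse events as safety endpoints, and SAP 4.3.3 names the Safety population for adverse events.
- SAP 4.3.14, which governs individual listings only, puts under mITT the DHEQ together with "Numeric Pain Rating Scale (NPRS), Numeric Rating Scale (NRS), and the Oral Hygiene Questionnaire (OHQ").

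SAP 4.3.12.2 says that NPRS is analysed by the same methods as the DHEQ endpoints. It names no population.

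On timing, the Schedule of Activities (protocol 1.2) has NPRS but no DHEQ at Week 1 (Day 7, ±1 day) and at "Week 2 Day 14 (±2 days"). The first post-baseline DHEQ is at "Week 4 Day 28 (±7 days"). On missing data, SAP 4.3.15 says "The MMRM approach will include all participants in the mITT population in the analysis".

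**The concern.** For the DHEQ endpoints the entry condition costs nothing, because a participant with no post-baseline DHEQ has no change score to contribute. For NPRS it discards outcomes that were observed. Whether a Week 1 pain score counts depends on whether the participant was still engaged at least two weeks later.

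The MMRM cannot repair this, because these participants are removed before it is fitted. If leaving depends on the early pain scores, a model that kept those scores would be valid under the SAP's own missing-at-random assumption. A model without them need not be. The descriptive means, plots and >30% responder counts have no model behind them at all.

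What is at stake is limited: the early part of one descriptive secondary endpoint. NPRS is, however, the only outcome scale scheduled at Weeks 1 and 2, so it carries whatever is reported about early response.

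**Working it through.** **The plan's own figures.** The documents give none for NPRS or for exclusions from mITT. The figures they do give reproduce: 400/(1 - 0.20) = 500 enrolled; power of the one-sample t-test at n = 400 and effect size 0.2 is 97.9%, which satisfies the stated minimum of 90%; CI half-widths are 1.96 × 30/√400 = 2.94 and 1.96 × 50/√400 = 4.90, matching 3 and 5. All concern the DHEQ Total Score and do not depend on the NPRS population.

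**Windows (protocol 1.2).** Week 1 NPRS: Days 6-8. Week 2 NPRS: Days 12-16. First DHEQ: Days 21-35. The latest Week 2 NPRS comes 21 - 16 = 5 days before the earliest DHEQ, so the gap always exists.

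**Formula.** Let f be the share of participants with NPRS data at a visit who are excluded, and D the difference in mean change between those kept and those excluded. The shift in the visit mean is f × D. This is exact for raw means and approximate for the MMRM. The documents give neither dropout timing nor D, so both are assumed below.

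**Uniform dropout (assumed).** The full 20% of 500 is spread evenly over 168 days from Day 0, a loss of 100/168 participants per day. Anyone still present is assumed to complete the DHEQ. Low ends pair the latest NPRS day with Day 21; high ends pair the earliest NPRS day with Day 35.

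| | Week 1 low | Week 1 high | Week 2 low | Week 2 high |
|---|---|---|---|---|
| Days at risk | 21 - 8 = 13 | 35 - 6 = 29 | 21 - 16 = 5 | 35 - 12 = 23 |
| Excluded (days × 100/168) | 7.7 | 17.3 | 3.0 | 13.7 |
| With NPRS data (500 - NPRS day × 100/168) | 495.2 | 496.4 | 490.5 | 492.9 |
| f | 1.56% | 3.48% | 0.61% | 2.78% |
| Shift, D = 1 point | 0.016 | 0.035 | 0.006 | 0.028 |
| Shift, D = 2 points | 0.031 | 0.070 | 0.012 | 0.056 |
| Responder rate, assumed 20-point gap | 0.31 pp | 0.70 pp | 0.12 pp | 0.56 pp |

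The 20% is a ceiling, and some of it can be spent before Day 0: "Baseline activities must be completed by participant within 14 days of enrollment", and Day 0 comes only when receipt of the toothpaste is confirmed. If 5 of the 20 points go before Day 0 (assumed), 75/168 participants are lost per day. That gives 5.8-12.9 excluded at Week 1 and 2.2-10.3 at Week 2.

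**Front-loaded attrition (assumed).** With 2-10% excluded and a gap of 1-2 points, the shift runs from 0.02 × 1 = 0.02 to 0.10 × 2 = 0.20 points.

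**Scale.** With an assumed SD of change of 2-3 points and n of about 480, the 95% CI half-width is 1.96 × 2/√480 = 0.18 to 1.96 × 3/√480 = 0.27 points. The uniform-dropout shifts lie well inside this. The top of the front-loaded range is about the same size.

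**The case against.** The rule is stated consistently in three places and is not hidden. One common set keeps the NPRS and DHEQ tables on the same participants, which is a legitimate aim. That explains the choice, but it does not answer the loss of observed scores.

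The plan also discloses part of the loss. SAP 4.3.5 reports the Safety and mITT counts, the reasons for discontinuation and each participant's population assignment. Protocol 12.2.2 adds a listing of reasons for exclusion from a population, where applicable. Readers can therefore see the Safety-minus-mITT difference, which caps the number affected. They will not see how many of those participants had post-Baseline NPRS, or what they scored.

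The link from NPRS to mITT is inferred. Neither document defines efficacy data, and protocol 9.3 puts the pain assessment under a heading that includes safety. Even so, mITT is the natural reading, because no text gives NPRS another population.

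A reader might infer that the SAP withdrew the protocol's provision for further missing-data sensitivity analyses, since SAP 4.3.15 does not repeat it and the SAP defines none. That does not follow. The SAP says that it elaborates the protocol, so protocol 12.3.6 still stands. It leaves such analyses to data review, which is not pre-specification.

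**Conclusion.** Minor. It is certain from the definitions and the visit windows that early NPRS scores are excluded when no post-baseline DHEQ follows. The consequence is not certain: the direction is unknown, and the bias is zero if those excluded do not differ from those kept.

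Under uniform 20% dropout, the Week 1 or Week 2 mean shifts by at most about 0.07 points at a 2-point gap. Under front-loaded attrition the range is 0.02-0.20 points. Dropout timing, the gap and the NPRS SD are all assumptions.

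A reader might infer that early leavers had less relief, so that early improvement is overstated. The documents contain nothing about early leavers and do not support this. Nor does the point reach the primary DHEQ analysis, the power statement or the success statement, which rests on OHrQoL.

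**What to change.** Before database lock:

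- In SAP 4.3.3, define an NPRS analysis set: Safety participants with a Baseline NPRS and at least one post-Baseline NPRS.
- In SAP 4.3.12.2, repeat the NPRS MMRM, summaries and >30% responder count in that set as a supplementary analysis.
- Report the number of participants with post-Baseline NPRS but no post-baseline DHEQ, and extend the NPRS listing in SAP 4.3.14 to include them.

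Keep the DHEQ-based mITT for the DHEQ endpoints.

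The cost is about a sentence per SAP section and no new data. The edit fits protocol 12.3, which leaves secondary-endpoint detail to the SAP, and protocol 12.3.6. Making the new set the main NPRS set is optional; it would need an amendment to protocol 12.2.1 with prospective IRB approval (protocol 13.3.1), which an effect this small does not require. The downside is that NPRS and DHEQ tables will show slightly different N. Participants with no post-Baseline NPRS remain excluded either way.
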